3.1. Study Endpoints

The primary endpoint is the median Complete Protection Time (CPT) of the repellent products. The CPT is defined as the time between application of the repellent product and the occurrence of the first probe or bite in a 1 minute test, followed by a confirmatory probe or bite within 30 minutes.

The secondary endpoint is an assessment of the products Protective Efficacy (PE) over time. Protective Efficacy over time will be expressed as the percentage of midges probing or biting at hourly intervals from the time of the repellent application to the end of the test (when 50% or more midges are probing or biting the test arm vs. untreated control, or 12 hours).

3.2. Risks and Benefits

3.2.1. Midges

Participants will be exposed to insect bites and may experience some irritation and itching. The midges are reared in insectaries and have been in culture for many years and are pathogen free. In order to minimise the risk of infection the following steps have been taken:

- Midges used in the test are 3-8 days old and have never had a blood meal.
- One cage of midges is used on one volunteer only and after the test, those midges are destroyed. Therefore, no two volunteers are ever bitten by the same midges and the midges are never returned to the colony.
- There will be a minimum of 72 hours between product tests in order to minimise any possibility for sensitization to midges bites

3.2.2. Product

p-Menthane,3-8-diol (PMD) is a recommended active ingredient, which has been evaluated for safe use by the U.S. Environmental Protection Agency (USEPA)¹. According to the USEPA laboratory exposure of animals to the active ingredient, PMD, this resulted in no adverse effects except eye irritation. The Product Safety Data Sheets for the PMD product classify PMD as seriously irritating to eyes. The eye irritation potential of the finished product formulation has not been studied; therefore as a precaution, the products will be handled in the same way as the active ingredient. The researcher and participant must wear eye protection during application of the product and the potential for eye irritation is described in the Participant Information Sheet. Correct handling of the product by the researcher according to ARC-SOP-006 "Safe Handling and Application of Insect Repellent PMD" will avoid risks associated with the eyes. Participants will be excluded if they have a known allergy to any of the product ingredients, or any skin condition, which may affect their reaction to the product.

The active ingredient, Picaridin, has been classified as potentially mildly irritating/uncomfortable to the eyes – participants and researcher will wear safety glasses during handling of the products and the participants will be warned about the potential for irritation during the Informed Consent Procedure. Participants will also be excluded if they have a known allergy to any of the product ingredients, or any skin condition which may affect their reaction to the product.

Specifically, for both products, the staff member should:

- Handle and apply small volume of product that was beforehand calculated for each participant
- Apply the products in a well ventilated room (air extractors and vents are available and can be turned on in the laboratory when the product is applied) to avoid risks associated with potential respiratory track irritations
- Ensure that the eyes of the staff member and the participants are protected with safety glasses when the products are being measured and applied;
- Remind the participant not to transfer the repellent from their arm to their face, either directly, or by touching their arm and then their face. Gloves are required during testing;
- Rinse with clean water if the eyes come into contact with the repellent, and seek medical advice from a first-aider (dial 0 to ask reception or look up 'First aid' in the LSHTM Telephone Book)
- There will be a minimum of 72 hours between product tests in order to minimise any possibility for sensitization to products over time.
- Report any adverse events

There is no evidence to suggest that the active ingredients present any risk to pregnant or lactating women or the unborn child. However, since participants will be exposed to and may experience increased sensitivity to midge bites, pregnant women will not be included in the study.

General risks to participants associated with involvement in this study will be addressed by adhering to ICH GCP², the Declaration of Helsinki³, the Data Protection Act⁴ and all applicable regulatory requirements.

There will be no benefit to participants. The results of this study will inform the products labelling.

4. Participant Entry

4.1. Screening Procedures

Volunteers will be consented prior to any screening procedures being undertaken. Volunteers who do not meet the criteria for eligibility will be excluded. In order to assess sensitivity in those volunteers who claim not to be sensitive to insect bites, volunteers will be given a bite test using the midge species used for testing. This will involve administering one *C. nubeculosus* bite and monitoring the reaction to the bite for up to 72 hours. Volunteers whose reaction (area of wheal) is larger than 1 cm, or if the participant scores their itchiness or redness as 3 out of 3 (with "1" being "no itchiness/redness", "2" being "some itchiness/redness", and "3" being "very itchy/red"), they will be unable to test with that midge species. Volunteers who fail the screening procedures will be advised that they will not proceed in the study and will be withdrawn and replaced.

4.2. Inclusion Criteria

Volunteers will be healthy individuals and chosen based on their insensitivity to the bites in order to limit any itchiness or discomfort.

Volunteers will be included in the study if they meet all of the following criteria:

- Able and willing to give fully informed consent;
- Able to understand and comply with the study procedures;
- Consider themselves to be in good general health;
- Male or female;
- Aged 18 to 65 years;
- Non-smokers or willing to refrain for 12 hours prior to and during each test;
- Willing to undergo a bite test with *C. nubeculosus* midges with up to 72 hour follow-up.

Volunteers will be advised not to apply any cosmetics associated with a strong scent, such as perfume, hand cream, body wash, or scented. Additionally, volunteers will be asked not to drink alcohol or consume spicy foods, i.e. curries, chillies and garlic and to not to engage in vigorous exercise for the 12 hours prior to the tests. This will be verified with the participants prior to the commencement of any tests.

4.3. Exclusion Criteria

Volunteers will be excluded from the study if they meet any of the following criteria:

- Suspected or known to be sensitive or allergic to midge bites;
- Participated in an interventional study (other than a biting insect challenge study) in the previous 3 months;
- Participated in a biting insect challenge study in the previous 72 hours;
- Aware of having any cardiovascular or respiratory disorder (whether active or inactive) (e.g. asthma);
- Individuals with localized skin disorders affecting the forearm;
- Allergic to any of the test product ingredients;
- Extensive tattooing or other condition of the forearm which would make interpretation of the bite test results difficult;
- Women who are pregnant, nursing or intending to become pregnant;
- Previous anaphylaxis.
- Aware of having a compromised immune system; (an immune system that is temporarily or permanently incapable of working at full capacity);
- Phobia of flying insects;
- Travelled to a mosquito-borne disease endemic area in the last 3 months.

4.4. Withdrawal Criteria

Participants can stop at any time without giving a reason for withdrawing. Data collected to the point of withdrawal will be used in the analysis of the study, unless the participant requests that their data is not used, in which case it will be removed from the database. Participants may also be removed at the discretion of the Chief Investigator, where continued participation may affect the safety of the participant or where there is a development of any condition which might interfere with study participation.

5. Randomisation and Enrolment

Volunteers will be recruited through standard recruitment methods, including emails, posters, leaflets and other advertising routes to staff and students of LSHTM and other members of the public. Volunteers will be fully informed before the study and it will be made clear that they can withdraw from the study at any time. Volunteers will be given and asked to read the Participant Information Sheet and Product Information Sheet which describes the tests which they will take part in, and a consent form which must be signed before the test begins.

6. Treatments

NEO-INNOVA HEALTHCARE LIMITED will provide two products to be tested containing 35% and 40% PMD, and one positive control containing 20% Picaridin. The positive control product is currently marketed as a midge repellent, while PMD is a recommended active ingredient, which has been evaluated for safe use by the U.S. Environmental Protection Agency (USEPA)¹. Therefore, humans have already used the products. The products will be applied at a rate of 1.67 $\mu\text{l}/\text{cm}^2$. The products will be applied to the measured forearm of each participant. This dose does not exceed the maximum daily limit for PMD or Picaridin.

7. Safety Reporting for Non-Drug Trials

7.1. Definitions

Term	Definition
Adverse Event (AE)	Any untoward medical occurrence in a patient or study participant
Serious Adverse Event (SAE)	A serious event is any untoward medical occurrence that: Results in death Is life-threatening Requires inpatient hospitalisation or prolongation of existing hospitalisation Results in persistent or significant disability/incapacity Consists of a congenital anomaly or birth defect Other 'important medical events' may also be considered serious if they jeopardise the participant or require an intervention to prevent one of the above consequences.

Medical judgement should be exercised in deciding whether an AE is serious in other situations. Important AEs that are not immediately life-threatening or do not result in death or hospitalisation but may jeopardise the participant or may require intervention to prevent one of the other outcomes listed in the definition above, should also be considered serious.

7.2. Reporting Procedures

All adverse events and serious adverse events should be reported. Depending on the nature of the event the reporting procedures listed below should be followed. Any questions concerning adverse event reporting should be directed to the chief investigator in the first instance.

7.2.1. Non serious AEs

All adverse events should be recorded on the Adverse Event Record Form (Appendix 1) and Adverse Event Monitoring Questionnaire (Appendix 2) and entered into a spreadsheet and stored on the "I" drive with access limited to the *arctec* study staff. All adverse events will be reported to NEO-INNOVA HEALTHCARE LIMITED. Depending on the nature of the event the reporting procedures below should be followed, see Appendix 3 for a flowchart of safety reporting.

In the event of minor adverse reactions such as localised skin redness and swelling, volunteers will be directed to contact the nearby GP surgery at [name] ([contact]) or their own GP.

7.2.2. Serious AEs

Regardless of the relation of the adverse event to study participation, the event must be reported as a serious adverse event if it meets any of the definitions in section 7.1. AE questionnaires meeting the SAE definition will be

submitted to [name] within 24 hours. SAEs that are assessed by the CI as being both related and unexpected must be reported to the LSHTM EC within 15 days of the CI becoming aware of the event.

In the case of a severe reaction such as anaphylaxis, it will be treated as an emergency and an ambulance will be called immediately by dialling 999 directly from a mobile, or 555 from an internal phone (this is the emergency line at reception who will then dial 999). In addition, a trained First Aider within the [name] building will be called. Designated First Aider is [name] ([name]), but if they are unavailable First Aiders are contactable through internal phones by typing in 'first aid' to the internal phone book which will bring up a list of registered First Aiders. All *arctec* staff ([name] [name], [name] [name], [name] [name]) and some of the other insectary staff ([name] [name]) have also been trained in anaphylaxis.

In the event of an acute allergic reaction, a trained First Aider within the [name] building will be called and the member of staff present will remove the trigger if possible. This will include removing any biting mosquitoes and washing the product off the participant's arm.

8. Test methodology

Female midges will be host-seeking, of uniform age and 3-8 days post-emergence. Active host-seeking females will be selected to ensure a good response from the test midges using an aspirator or an appropriate airflow apparatus.

Fifty female midges will be placed into a cage 20x20x20cm inside the testing room at least one hour before the test commences. Testing should be conducted in a testing room maintained at 25±2°C and 80% RH.

The researcher will verify that the participant has adhered to the pre-testing instructions. Non-compliant participants will be unable to participate in the test on that day and will be booked in for another appointment.

8.1. Midge Fitness Check and control test (combined)

Before the start of each test, the participant will insert a bare (control) left arm into the cage for 1 minute to assess biting activity of the midges. Only cages with at least 10 midges landing within one minute will be used in the tests. This same procedure is used to assess whether volunteers are attractive to the midges. The number of midges probing or biting the arm after 1 minute will be counted and recorded (to provide biting rate data of the control test for the Protective Efficacy endpoint) and the arm removed from the cage.

8.2. Product application

The products will be applied to the forearm between the wrist and elbow. Volunteers' forearm surface area is estimated using the WHO protocol for testing skin repellents below:

$$Area = \frac{1}{2} (C_W + C_E) \times D_{EW}$$

Where C_W is the circumference of the wrist; C_E is the circumference of the elbow; and D_{EW} is the distance between the wrist and elbow in centimetres (cm). The dose is expressed using $\mu\text{l}/\text{cm}^2$. The appropriate dose is then measured using a micropipette or balance and applied to the arm using a gloved finger.

8.3. Complete Protection Time

The repellent product will be applied to the right arm of the participant. A combined fitness check and control test is conducted as described in section 8.1. Immediately after, the right (treated) arm is inserted into the cage for 1 minute. The number of midges probing or biting the arm after 1 minute will be counted and recorded. A further hour post-application of the repellent product, the left arm (control) of the volunteer is again inserted into the cage. The number of midges probing or biting the arm after 1 minute will be counted and recorded and the arm removed from the cage. If less than 10 midges land on the untreated arm during this 1 minute test the cage will be refreshed with new midges and the test repeated. Immediately after, the right (treated) arm is again inserted into the cage for 1 minute. The number of midges probing or biting the arm after 1 minute will be counted and recorded. This procedure will be repeated at hourly intervals throughout the test.

If at any stage, more than one midge probes or bites on the treated arm in the 1 minute test, this represents the end of the testing for Complete Protection Time. If, at any stage, one midge probes or bites on the treated arm in the 1 minute test the test will be repeated half an hour later. If there is a confirmatory probe or bite during the test, this represents the end of the testing for Complete Protection Time but testing for Protective Efficacy (as described in section 8.4) will continue at hourly intervals, with the next test taking place 30 minutes later. If there is no confirmatory probe or bite during this test, testing will resume, with the next test to take place 30 minutes later. All testing for Complete Protection Time and Protective Efficacy must be conducted at hourly intervals.

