APPENDIX 3: FLOWCHART FOR SAFETY REPORTING24

APPENDIX 4: SAMPLE SIZE CALCULATION FOR A COMPARISON TRIAL BETWEEN A POSITIVE CONTROL AND TWO MIDGE REPELLENT PRODUCTS.....25

1. Introduction

Mosquitoes, midges and other biting insects are vectors of extremely important diseases such as malaria, yellow fever, filariasis and many viruses and also may be of great nuisance value. The use of repellent products can provide added personal protection from disease transmission and nuisance bites. New effective repellents would offer an additional option for protection against biting insects. The tests carried out by *arctec* provide important information on the effectiveness of skin repellents, which will be used for label claims to accurately inform consumers and registration purposes.

The aim of this study is to determine the effectiveness of two topically applied insect repellent products provided by NEO-INNOVA HEALTHCARE LIMITED and one positive control containing the UK repellent brand 'Smidge'.

2. Objectives

Primary objective: To determine and compare the median complete protection time (CPT) of two insect repellent products and a positive control against *Culicoides nubeculosus* (midges).

Secondary objective: To determine and compare the protective efficacy of two insect repellent products and a positive control against *Culicoides nubeculosus* (midges).

3. Study Design

This is a single-centre, single-arm study with all participants testing two formulations containing PMD and a positive control product containing Picaridin. The control for each test is an untreated arm. There is no blinding or randomisation employed, since the outcome measures are based on midge behaviour. Repellent product testing takes place in a laboratory setting using 7 participants (preferably gender balanced). Each participant will test both PMD formulations and a positive control product (see section 8).

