9.2. Data analysis

The endpoint for Complete Protection Time will be time to treatment failure for each participant test. Treatment failure is the time at which the product no longer provides complete protection, which is determined as the time at which one probe or bite occurs in a 1 minute test, followed by a confirmatory probe or bite within 30 minutes. Using IBM SPSS Statistics 20, the times to treatment failure will be analysed using Kaplan-Meier Survival functions, and from these the median Complete Protection time and 95% confidence intervals will be calculated.

A linear regression will be used to compare the mean complete-protection time for the tested repellents. As a sensitivity analysis we will use linear regression to estimate the mean CPT difference between groups, but we will generate robust standard errors by relaxing the assumption of independence of observations between the same participant within the study, allowing for correlation between observations from the same participant in the variance-covariance matrix.

The Protective Efficacy over time from application will be calculated using the formula below at each hour and presented as a summary table and graph. Using IBM SPSS Statistics 20, the PE will be analysed using a two-way analysis of variance followed by Tukey's tests or generalised linear model.

$$PE = \frac{\text{Midges probing on control} - \text{Midges probing on treatment}}{\text{Midges probing on control}} \times 100$$

Adverse Events will be tabulated and included in the study report. Adverse events occurring after the end of participant participation but before the end of the study will be listed separately.

10. Safety and Data Monitoring

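### With the product always on the right arm and the control always on the left, absolute Protective Efficacy cannot be separated from any right-left difference in midge probing

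*Combined protocol and SAP*

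**What the plan says.** Section 8.3 fixes the treated side: "The repellent product will be applied to the right arm of the participant". Section 8.1 fixes the control side before each test: "the participant will insert a bare (control) left arm into the cage for 1 minute". Section 8.3 repeats this at each hourly test, where "the left arm (control) of the volunteer is again inserted into the cage". The order of insertion is also fixed, control first: "Immediately after, the right (treated) arm is inserted into the cage for 1 minute".

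Section 3 has every participant test all three products and gives one general statement on allocation: "There is no blinding or randomisation employed, since the outcome measures are based on midge behaviour". It does not discuss arm side. No section alternates or balances the side, or takes an untreated count on the right arm. The data list in Section 10.3 has only a control-arm and a treated-arm count.

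Section 9.2 computes PE hourly as control count minus treatment count, divided by control count. The analysis is a two-way analysis of variance with Tukey's tests, or a generalised linear model, and no side term is named. Sections 3.1 and 8.4 end PE testing when probing on the treated arm reaches half that on the control arm, or at 12 hours.

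**The concern.** PE is one minus the ratio of treated count to control count. In this plan the first is always a right-arm count and the second always a left-arm count, in all 7 participants and at all visits. If midges probe untreated right and left arms at different rates, for instance because of how the arm is presented in the cage, that difference enters PE as if it were a product effect. A side term in the model would not help, because side and treatment coincide in every observation. More participants would not help either, because the bias does not shrink with sample size.

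What is at stake is the absolute level of PE. The secondary objective is to determine PE as well as to compare it, and Sections 1 and 3.2.2 say that the results will support label claims. The 50% stop for PE testing rests on the same ratio.

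**Working it through.** **Inputs from the documents.** There are 7 participants and three products per participant, all applied to the right arm (Sections 3 and 8.3). PE = (control − treatment)/control (Section 9.2). PE testing stops at 50% (Section 8.4). The documents give no figure for a side difference, so there is no plan figure to reproduce. The sample size of 7 in Appendix 4 concerns Complete Protection Time (CPT) and is unaffected.

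**Assumption.** Let R be the ratio of right-arm to left-arm probing on untreated skin. R is not in the documents; 0.8 to 1.25 is used as an illustration. R = 1 means no side effect.

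**Step 1: effect on absolute PE.** If PE is the true value on a same-arm basis, the treated right-arm count is R × (1 − PE) times the left-arm control count. Hence observed PE = 1 − R(1 − PE).

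| True PE | R = 0.8 | R = 1 | R = 1.25 |
|---|---|---|---|
| 50% | 1 − 0.8 × 0.5 = 60% | 50% | 1 − 1.25 × 0.5 = 37.5% |
| 80% | 1 − 0.8 × 0.2 = 84% | 80% | 1 − 1.25 × 0.2 = 75% |
| 90% | 1 − 0.8 × 0.1 = 92% | 90% | 1 − 1.25 × 0.1 = 87.5% |

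The error shrinks towards zero as true PE approaches 100%.

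**Step 2: effect on the 50% stop.** The stop is met when R(1 − PE) = 0.5, so true PE at the stop is 1 − 0.5/R. This is 37.5% at R = 0.8 and 60% at R = 1.25.

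**Step 3: effect on product comparisons.** All products share the right arm, so for products A and B the observed difference is R × (PE of A − PE of B). A true 10-point difference reads as 8 points (R = 0.8) to 12.5 points (R = 1.25). A zero difference stays zero and the sign is kept, provided that R is constant within a participant.

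**Step 4: effect on CPT.** Sections 3.1 and 9.2 score CPT from probes or bites on the treated arm. The left-arm count enters only through the check for at least 10 landings, so the right/left ratio is not part of the calculation.

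**Step 5: what a 4/3 split would do.** A participant treated on the left has ratio 1/R. At R = 0.8 this is 1.25, so at true PE of 50% a participant treated on the right reads 60% and one treated on the left reads 37.5%.

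- Four on the right: (4 × 60 + 3 × 37.5)/7 = 352.5/7 = 50.4%.
- Three on the right: (3 × 60 + 4 × 37.5)/7 = 330/7 = 47.1%.
- Fixed right arm: 60%.

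These means take all seven participants as having a reading at that hour.

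**The case against.** The strongest reply is that nothing in the documents shows or implies a right-left difference. R may be 1, in which case the bias is nil. This stands, and it limits how much weight the point can carry.

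It is also true that the effect need not run the same way in everyone. An asymmetry tied to hand dominance would reverse in left-handed participants, and personal asymmetries would tend to average out. Only a systematic side difference biases mean PE.

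Sampling noise at any one test is larger than the assumed bias. With Poisson counts of 10 on control and 5 on treated skin (assumed), the standard error of the ratio is 0.5 × √(1/10 + 1/5) = 0.27, or 27 PE points, against 10 to 12.5 points in Step 1. However, that noise averages down over tests and participants, and a fixed-side bias does not.

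A reader might infer that the primary endpoint or the ranking of products is compromised. The documents do not support this. CPT does not use the ratio, and all three products are tested on the same arm of the same participants.

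Finally, balancing sides is an incomplete remedy. Each participant's own 50% stop would still be shifted: at R = 0.8 it falls at true PE of 37.5% for those treated on the right and 60% for those treated on the left. The control arm would still always enter the cage first. Both objections stand and belong in the stated limits of the fix.

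**Conclusion.** The point holds for absolute PE. Side is completely aliased with treatment, and no planned analysis can separate them. For an assumed R of 0.8 to 1.25, the error is 10 to 12.5 points at a true PE of 50%, and 2 to 2.5 points at 90%. The 50% stop carries the same error. The size and direction in this trial are unknown, so the documents do not support a claim that PE will be overstated or understated.

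PE is the secondary endpoint. Comparisons of PE between products are at most rescaled, on the assumption that any side effect is constant within a participant. The primary CPT calculation and the sample size of 7 are untouched. This is a minor design weakness, worth correcting because the correction costs almost nothing.

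**What to change.** In Sections 8.1 and 8.3, replace the references to the right and left arm with treated arm and control arm. Add that the treated side is assigned by a list made before the first test (four participants on one side, three on the other) and kept the same for all three visits of a participant, so that product comparisons stay within one arm. Record the treated side in the case report form.

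The cost is a seven-line list and a few words in two sections, with no added tests or bites. If a side effect exists, absolute PE will vary slightly more between participants.

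The protocol should state two limits. Only the average shift in the 50% stopping time is reduced, not each participant's own shift. The control-first insertion order remains confounded with treatment.
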